18.2 Cell-associated HIV-1 DNA in participants prior to ART initiation

Pre-ART cell-associated HIV-1 DNA will be summarized using the same approach as week 48 CAHD.

Fold-changes (absolute change in the log₁₀-transformed measurements) from pre-ART measurement in CAHD will be summarized using a similar approach.

Correlations between selected immunology responses (IFNg+ and total response) and week 48 CAHD will be examined using Spearman correlation coefficient (primary analysis population) with and without controlling for the study group.

19 OTHER OUTCOME MEASURES

Analysis of other outcome measures will use the same approach as the secondary outcome measure. The following exploratory outcome measure(s) will be included in the primary analysis report:

19.1 Signs and symptoms of acute retroviral syndrome

Table: summarizing number (%) of participants and the signs and symptoms of acute retroviral syndrome reported in the database, by MedDRA SOC, PT, grade and study group.

19.2 Absolute CD4+ and CD8+ T-cell counts, CD4/CD8 ratio, and HIV-1 RNA prior to and after ART initiation

See section 13.

Other outcome measures from the protocol not listed here will be included in a separate report.

ACTG A5354
Primary Statistical Analysis Plan

[REDACTED]

[REDACTED]

[REDACTED]

[REDACTED]

[REDACTED]	[REDACTED]	[REDACTED]
[REDACTED] [REDACTED] [REDACTED] [REDACTED] [REDACTED]	[REDACTED] [REDACTED] [REDACTED] [REDACTED]	[REDACTED] [REDACTED]
[REDACTED]		[REDACTED]
[REDACTED] [REDACTED]	[REDACTED]	[REDACTED]
[REDACTED]		[REDACTED]
[REDACTED]	[REDACTED]	[REDACTED]
[REDACTED] [REDACTED] [REDACTED]	[REDACTED]	[REDACTED]
[REDACTED]	[REDACTED]	[REDACTED]
[REDACTED] [REDACTED]	[REDACTED]	[REDACTED]
[REDACTED]	[REDACTED]	[REDACTED]
[REDACTED] [REDACTED]	[REDACTED]	[REDACTED]
[REDACTED] [REDACTED]	[REDACTED] [REDACTED]	[REDACTED]
[REDACTED]	[REDACTED]	[REDACTED]
[REDACTED] [REDACTED]	[REDACTED]	[REDACTED]

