10.2.3.10 Signs and symptoms of acute retroviral syndrome

10.2.3.11 Absolute CD4+ and CD8+ T-cell counts, CD4/CD8 ratio, and HIV-1 RNA prior to and after ART initiation

6. Clinical Site Monitoring and Record Availability

In section 12.3, Clinical Site Monitoring and Record Availability, the remote monitoring language and reference listed below are being added to follow the first paragraph of subsection 12.3.1.

12.3.1 Site monitors under contract to the NIAID will visit participating clinical research sites to review the individual participant records, including consent forms, eCRFs, supporting data, laboratory specimen records, and medical records (physicians' progress notes, nurses' notes, individuals' hospital charts), to ensure protection of study participants, compliance with the protocol, and accuracy and completeness of records. The monitors also will inspect sites' regulatory files to ensure that regulatory requirements are being followed and sites' pharmacies to review product storage and management.

Monitoring visits may be conducted on-site or remotely. Remote visits may include remote source document verification using methods specified for this purpose by NIAID. Remote monitoring visits may be performed in place of, or in addition to onsite visits to ensure the safety of study participants and data integrity [85]. The site will make available study documents for site monitors to review utilizing a secure platform that is HIPAA and 21 CFR Part 11 compliant. Potential platform options include: Veeva SiteVault, site-controlled SharePoint or cloud-based portal, direct access to Electronic

Medical Record (EMR), and Medidata Rave Imaging Solution. Other secure platforms that are 21 CFR Part 11 compliant may be utilized, as allowed by the DAIDS Office of Clinical Site Oversight (OCSO).

FDA Guidance on Conduct of Clinical Trials of Medical Products During the COVID-19 Public Health Emergency: Guidance for Industry, Investigators, and Institutional Review Boards, March 2020, Updated on January 27, 2021. Accessed at: <https://www.fda.gov/media/136238/download>

7. Part 2 Study Schedule of the Sample Informed Consent of A5354v2

In the Study Schedule for Part 2 of the Sample Informed Consent of A5354v2 (dated 12/31/19), the approximate amount of blood to be collected at Step 2 entry and every 24 weeks until week 144 has been corrected to be consistent with the Revised Laboratory Processing Chart (revised date 10/23/20).

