6.4.6 Clinical Assessments

The results of baseline laboratory evaluations and urinalysis will be reviewed with each study participant as part of the clinical assessment at week 1.

Complete Physical Exam

At entry and the premature study/treatment discontinuation visits, a complete physical examination is to include at a minimum an examination of the skin, head, mouth, and neck; auscultation of the chest; cardiac exam; abdominal exam; and examination of the lower extremities for edema. The complete physical exam will also include signs and symptoms, diagnoses, and vital signs (temperature, pulse, and blood pressure per local standard of care).

Targeted Physical Exam

At the post-entry visits, a targeted physical examination is to include vital signs (temperature, pulse, and blood pressure) and is to be driven by any previously identified or new signs or symptoms, including diagnoses that the participant has experienced since the last visit.

Post entry, refer to [section 8.9](#) for collection requirements for pregnancy.

Height

Height will be recorded **per the SOE**.

Weight

Weight will be recorded **per the SOE**.

Signs and Symptoms

At **Step 1** entry, signs and symptoms of all grades that occurred within 30 days prior to entry must be recorded as medical history. Please refer to [section 7.2](#) for AE reporting requirements for post-entry signs and symptoms.

At Step 2 entry, record SAEs and chronic medical conditions per [section 6.4.4](#) for re-enrolled participants who completed the study under protocol Version 1.0.

Diagnoses

At **Step 1** entry, all diagnoses that are described in [section 6.4.4](#) must be recorded as medical history. Please refer to [section 7.2](#) for AE reporting requirements for post-entry diagnoses.

At Step 2 entry, record SAEs and chronic medical conditions per [section 6.4.4](#) for re-enrolled participants who completed the study under protocol Version 1.0.

Concomitant Medications

For post-entry, record new or discontinued concomitant medications for prophylaxis and treatment of opportunistic infections and other medical conditions since the last study visit, including actual or estimated start dates and stop dates.

ART Modifications

All modifications to ARV medications including initial doses, participant-initiated and/or protocol-mandated interruptions (**that are ≥ 7 days**), modifications, permanent discontinuations, and last doses on study will be recorded.

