7.2 Adverse Event **Collection** Requirements

Post-entry, all AEs must be reported on the eCRFs if the reporting criteria have been met.

- **All Grade ≥ 3 signs and symptoms**
- **All Grade ≥ 2 laboratory findings**
- **All targeted diagnoses (refer to the list on the A5354 PSWP)**
- **All AEs that led to a change in study treatment/intervention regardless of grade**
- **All AEs meeting SAE definition or EAE reporting requirement**

NOTE: Uterine pregnancy does not require reporting as an AE (unless other SAE criteria are met) but must still be recorded on the eCRFs.

NOTE: SAEs or events meeting EAE reporting requirements should also be entered into the DAIDS Adverse Experience Reporting System (DAERS), an Internet-based reporting system.

All AEs that are reported must have their severity graded. To grade AEs, sites must refer to the DAIDS AE Grading Table, corrected Version 2.1, July 2017, which can be found on the DAIDS RSC website at <http://rsc.tech-res.com/clinical-research-sites/safety-reporting/daids-grading-tables>.

Serious Adverse Events (SAEs)

An SAE is defined as any untoward medical occurrence that:

- **Results in death**
- **Is life-threatening**
- **Requires inpatient hospitalization or prolongation of existing hospitalization**
- **Results in persistent or significant disability/incapacity**
- **Is a congenital anomaly/birth defect**
- **Is an important medical event that may not be immediately life-threatening or result in death or hospitalization but may jeopardize the patient or may require intervention to prevent one of the events listed above.**

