Since characterization of Fiebig stage using samples at the time of ART initiation will be performed with results known within 12 weeks based on standardized, centralized testing, an estimated Fiebig group at enrollment based on inclusion criteria from [section 4.1.1](#), as shown in the table below will provide additional real-time monitoring for accruals into each study group. Each Fiebig stage from I through IV has a median duration of approximately 5 days, the Fiebig stage at 7 days prior to enrollment may be expected to advance by one or possibly two stages by the time of enrollment. Both Fiebig stage determinations (centralized tested or estimated by inclusion criteria) will be used to guide accrual once enrollment is completed in at least one Fiebig group. For instance, **Groups 2 and 3 have reached their enrollment target under protocol Version 1.0, thus enrollment is closed for those two groups.**

Table 10.5-1. Expected Fiebig Group Based on Inclusion Criteria ([section 4.1.1](#))

Inclusion Criteria #	Inclusion Criteria Details	Expected Fiebig Group
a	A detectable HIV-1 RNA obtained within 28 days prior to study entry AND a non-reactive HIV-1 antibody within 7 days prior to entry	Group 1 (Fiebig I-II)
b	ARCHITECT or GSCOMBO S/CO ≥ 10 within 7 days prior to entry AND a non-reactive HIV-1 antibody within 7 days prior to entry	Group 1 (Fiebig I-II)
c	ARCHITECT or GSCOMBO S/CO ≥ 1 within 7 days prior to entry AND a non-reactive HIV-1 antibody within 7 days prior to entry AND a known prior S/CO < 0.5 within 90 days prior to entry	Group 1 (Fiebig I-II)
d	ARCHITECT or GSCOMBO S/CO > 0.5 but < 10 within 7 days prior to entry AND a non-reactive HIV-1 antibody within 7 days prior to entry AND detectable HIV-1 RNA within 7 days prior to entry	Group 1 (Fiebig I-II)

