12 ADVERSE EVENTS

The protocol requires grading of events according to The Division of AIDS Table for Grading the Severity of Adult and Pediatric Adverse Events (DAIDS AE Grading Table), corrected Version 2.1, July 2017, which can be found on the DAIDS RSC website at <http://rsc.tech-res.com/clinical-research-sites/safety-reporting/daids-grading-tables>.

The protocol makes the following reporting requirements for signs and symptoms:

“At Step 1 entry, signs and symptoms of all grades that occurred within 30 days prior to entry must be recorded as medical history. Post-entry Grade ≥ 3 signs and symptoms and all signs and symptoms that led to a change in ART, regardless of grade”

The protocol makes the following reporting requirements for laboratory test abnormalities:

“At Step 1 entry, record all protocol-required laboratory values (performed by local laboratories) with exception of the urinalysis, regardless of grade. For post-entry assessments, record all laboratory values for creatinine, CrCl, AST (SGOT), and ALT (SGPT) regardless of grade. Post-entry Grade ≥ 2 laboratory findings and all laboratory findings that led to a change in ART, regardless of grade”

NOTE: Creatinine clearance should be graded using the categorical mL/min values from the DAIDS 2.1 toxicity grading tables, which begins with values below 90 mL/min. The percent change criteria will not apply to A5354. In Step 2, only creatinine clearance greater than Grade 2 should be reported.

The protocol makes the following reporting requirements for diagnoses:

“At Step 1 entry, all diagnoses that are described in protocol section 6.3.4 (Acute HIV-1, bone fractures, coronary heart disease, cancer, diabetes, tuberculosis, chronic hepatitis B or C, renal disease) must be recorded as medical history. Post-entry, record all targeted diagnoses (see list on the A5354 PSWP) and diagnoses that led to a change in ART.

NOTE: Uterine pregnancy does not require reporting as an AE (unless other SAE criteria are met) but must still be recorded in the eCRFs.”

Additionally, all AEs meeting the SAE definition or EAE reporting requirements, or led to a change in study treatment, must be reported.

For the purpose of ongoing safety monitoring occurring within A5354, the following data summaries will be provided at each interim analysis, separately for Step 1 and Step 2:

Table: summarizing number (%) of participants and the adverse events reported in the database, by MedDRA SOC, PT, grade and study group.

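### SAP 19.1 tabulates acute retroviral symptoms by Fiebig group with no time window, although recording narrows at entry and infected time before entry differs by group

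*SAP*

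**What the plan says.** The second letter of amendment to Protocol Version 2.0 adds "Signs and symptoms of acute retroviral syndrome" as other outcome 10.2.3.10. It lists no change to how symptoms are collected. SAP 19 brings the outcome into the primary analysis report, and SAP 19.1 specifies counts and percentages of "signs and symptoms of acute retroviral syndrome reported in the database, by MedDRA SOC, PT, grade and study group". It gives no window and does not separate events before and after entry.

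Two recording rules feed that database:

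- **Before Step 1 entry.** Protocol 6.4.6 requires that "signs and symptoms of all grades that occurred within 30 days prior to entry must be recorded as medical history".
- **After entry.** Protocol 7.2 and SAP 12 set the general threshold at Grade 3 or higher. Lower grades are kept in specified cases: SAP 12 adds "all signs and symptoms that led to a change in ART, regardless of grade", and Protocol 7.2 lists "All AEs that led to a change in study treatment/intervention regardless of grade" and "All AEs meeting SAE definition or EAE reporting requirement". Targeted diagnoses are also recorded, from a list held outside these documents.

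Study group is the Fiebig stage at ART start, determined by central testing (SAP 2.1 and 4.1). On timing, Protocol 10.5 states: "Each Fiebig stage from I through IV has a median duration of approximately 5 days". Protocol 2.1 gives about 3 to 5 days per stage for the same stages.

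**The concern.** The variable that defines the groups also fixes when the all-grade rule stops. A Group 1 participant enters soon after infection becomes detectable. A mild fever or rash that starts a few days later will usually meet none of the post-entry reporting criteria. The same illness in someone who enters at a later stage may fall wholly before entry and be recorded at any grade.

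Read side by side, the columns of the SAP 19.1 table could then show differences in mild symptoms that reflect when recording narrowed, not how the illness differs by stage. Because the table goes into the primary analysis report, such a difference could be described as a clinical feature of Fiebig stage.

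**Working it through.** The plan gives no figure on this point to reproduce. The check sets the recording rules against the timing of entry.

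**1. Infected time before entry.** Let d be the length of each of Fiebig I to IV, 3 to 5 days (Protocol 2.1 and 10.5). Days are counted from the start of Fiebig I.

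- Group 1 (I/II) enters between 0 and 2d: day 0-6 if d = 3, day 0-10 if d = 5.
- Group 2 (III/IV) enters between 2d and 4d: day 6-12 or day 10-20.
- Group 3 (V) enters from 4d onwards: from day 12 or day 20. The documents give no length for Fiebig V.

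**2. What the all-grade rule catches.** A short Grade 1-2 symptom with onset on day s, in a participant entering on day e, is caught if e - 30 ≤ s ≤ e. With d = 5:

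- Onset on day 12: caught in no Group 1 participant (latest entry day 10), in Group 2 if entry is on day 12-20, and in Group 3 if entry is by day 12 + 30 = 42.
- Onset on day 5: caught in Group 1 if entry is on day 5-10, in all of Group 2, and in Group 3 only if entry is by day 5 + 30 = 35.

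The first case favours recording in later groups. The second shows the lookback working against Group 3. A symptom that persists into the 30-day window would still be recorded, so the lookback loss concerns illness that has resolved.

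**3. Is the order of the groups fixed?** Illustration only, with d = 5. Assumptions that are not in the documents: entry uniform within each group's span, onset uniform over days 0 to L, and Fiebig V lasting V days. Worked case with L = 10 and V = 30:

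- Group 1: mean of e/10 over e = 0-10, which is 0.50.
- Group 2: every onset precedes entry and lies within 30 days, so 1.00.
- Group 3: e runs from 20 to 50. All onsets are caught for e = 20-30 (10 days), half on average for e = 30-40 (equivalent to 5 days), and none for e = 40-50. The share is (10 + 5)/30 = 0.50.

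| L (days) | Group 1 | Group 2 | Group 3, V = 30 | Group 3, V = 60 |
|---|---|---|---|---|
| 10 | 0.50 | 1.00 | 0.50 | 0.25 |
| 15 | 0.33 | 0.92 | 0.58 | 0.29 |
| 20 | 0.25 | 0.75 | 0.67 | 0.33 |

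Group 1 is below Group 2 throughout. Group 3 is below Group 2 in all six cases, below Group 1 in two and equal to it in one.

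**4. Second illustration.** A simulation with 400,000 draws per scenario used d = 3 or 5, normal onset with mean day 5, 10, 15 or 20 and SD 4, and V = 30, 60 or 90: 2 × 4 × 3 = 24 scenarios. The onset and V values are again assumptions.

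- Group 1 is below Group 2 in all 24, and lowest of the three in all 18 with mean onset at day 10 or later.
- With d = 5, mean day 15 and V = 30, the shares for Groups 1, 2 and 3 are 0.02, 0.50 and 0.82.
- With d = 5, mean day 5 and V = 60, they are 0.50, 0.98 and 0.25.
- Across all scenarios the ranges are 0.00-0.50, 0.01-0.98 and 0.17-0.89.

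Ranges this wide support no estimate of size. They support only that Group 1 is the group most plausibly under-recorded.

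**5. Does the plan allow a group comparison?** SAP 19 applies the secondary-outcome approach to other outcomes. SAP 18 sends binary outcomes to the primary approach. SAP 17.1 makes that pairwise Fisher's exact tests between groups. SAP 19.1 names no test, but nothing rules one out.

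**The case against.** **SAP 19.1 may mean pre-entry symptoms only.** A reader might infer that the table pools both periods, but the SAP does not say so. In the letter of amendment, neighbouring outcomes 10.2.3.7, 10.2.3.8, 10.2.3.9 and 10.2.3.11 name periods before and after ART, while 10.2.3.10 does not. SAP 19.2 names both periods and 19.1 does not. On a pre-entry reading the change in grade threshold plays no part. What stands then is unequal infected time before entry together with the 30-day lookback, and the window still needs stating.

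**Post-entry recording is not strictly Grade 3 or higher.** This is correct, given the any-grade routes in Protocol 7.2. The week 2 and week 8 calls also ask about Grade 2 or higher events and are documented on the eCRF (Protocol 6.3.3), though the documents do not say whether those answers reach the tabulated data. Loss of every post-entry Grade 2 event is therefore not established. A mild, self-limited symptom that triggers none of these routes can still go unrecorded.

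**The table is descriptive and exploratory, and already split by grade.** Objective 1.4.8 is to characterise acute infection, not to compare groups, and Grade 3 or higher can be read from the table as planned. This lowers the severity. It does not stop readers comparing the Grade 1-2 rows across columns, nor close the route to testing.

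**Conclusion.** The concern holds as a minor point. If SAP 19.1 is followed literally, Grade 1-2 and any-grade symptoms are set side by side by study group under unequal ascertainment. The bias is most plausibly under-recording in Group 1. That inference rests on a share of symptoms starting after Group 1's early entry, and the documents give no onset timing.

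Two stronger readings are tempting and unsupported. One is that Groups 1 and 2 are both under-recorded; the position of Group 2 relative to Group 3 changes with the assumptions. The other is that the table will show symptoms rising with Fiebig stage; that needs Group 3 to be almost fully captured, which the 30-day lookback and the unstated length of Fiebig V do not allow one to assume. No size can be derived. The primary CAHD analysis and the secondary outcomes are unaffected.

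**What to change.** In SAP 19.1:

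1. Show two tables by study group: pre-entry events (all grades, 30 days before Step 1 entry), titled as symptoms present up to ART start, and post-entry events through a stated early visit such as week 4.
2. Do not test or interpret group differences in Grade 1-2 or any-grade symptoms pooled across entry. Limit any comparison that spans entry to Grade 3 or higher, and note that post-entry events may be ART-related; Protocol 8.2 to 8.6 anticipates, for example, rash, nausea and headache on treatment.
3. Footnote both tables: time since infection at entry differs by group by design, and the pre-entry lookback is 30 days.

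A window that is common relative to entry does not equalise time since infection, so the footnote is needed even for the Grade 3 or higher comparison.

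The cost is SAP wording and one extra table from data already collected. The downside is fewer events and less precision in the Grade 3 or higher comparison. New symptom collection is not proposed: Protocol 2.1 reports 168 of the planned 196 participants enrolled by 22 May 2019, and SAP 3.2 says the accrual and baseline sections were reported in July 2020, so it would probably come too late.
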